### **Sample Size Needs**

Respondents will be approximately 60 US adults ages 18+ who identify as Latino. We powered the study to detect an effect size of  $d=0.27$  or larger, assuming 4 repeated measures, 80% power, a correlation among repeated measures of 0.60, and a nonsphericity correction of 1. This effect size is conservative given that our recent meta-analysis found a large effect size for the impact of pictorial (vs. text) warnings on dwell time ( $d=1.74$ ) in eye tracking studies.

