## **Statistical Considerations**

### **General Principles**

We will use a two-sided critical alpha of 0.05 to conduct all statistical tests. We will use complete case analysis to handle any missing data in analyses of the primary and secondary outcomes.

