### **Primary Outcome**

Primary outcome: Amount of time spent looking at the FOP sodium label (i.e., dwell time). This outcome will be measured using eye tracking technology.

*Hypothesis 1.* We predict that each of the three intervention FOP sodium label types will elicit higher dwell time on the FOP sodium label compared to the control. We predict that the pictorial FOP sodium label will elicit higher amounts of dwell time than the icon label, the icon label will elicit higher amounts than the text-only label, and the pictorial label will elicit higher amounts than the text-only label.

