#### 1. Analyses of the primary outcome:

- a. We will run a mixed effects linear regression model, regressing dwell time on an indicator variable for FOP sodium label type. The control label will be the reference group. The model will treat the intercept as random. We will use pairwise comparisons to compare predicted means for the three intervention FOP sodium label types to each other.

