#### 2. Analyses of the secondary outcomes:

- a. We will use the same modeling approach used in the primary outcome to examine the impact of FOP sodium label type on secondary outcomes.

For analyses of primary and secondary outcomes, we will use the Benjamini-Hochberg method to correct for multiple tests. These analyses will treat each outcome as a family of tests, correcting for the six tests within each outcome and controlling the false discovery rate at 0.05.

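### The 80% power quoted for d = 0.27 fits an omnibus F test that the plan does not run; a planned pairwise contrast of that size has about 64% power before multiplicity correction

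*Combined protocol and SAP*

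**What the plan says.** Under Sample Size Needs the plan says "Respondents will be approximately 60 US adults ages 18+ who identify as Latino". It continues "We powered the study to detect an effect size of" d = 0.27 or larger, "assuming 4 repeated measures, 80% power, a correlation among repeated measures of 0.60, and a nonsphericity correction of 1". It calls this conservative because the team's meta-analysis "found a large effect size for the impact of pictorial (vs. text) warnings on dwell time" (d = 1.74). The paragraph does not say which test the power refers to, which SD standardises d, or whether multiplicity was taken into account.

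The analysis is by individual contrasts:

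- **Primary Outcome, Hypothesis 1:** each of the three labels is predicted to exceed control, and the labels are ordered among themselves, for example "the pictorial FOP sodium label will elicit higher amounts of dwell time than the icon label".
- **Analyses of the primary outcome:** a random-intercept linear model with control as reference, and then "We will use pairwise comparisons to compare predicted means for the three intervention FOP sodium label types to each other".
- **Analyses of the secondary outcomes:** the same model for each secondary outcome. Benjamini-Hochberg is applied to primary and secondary outcomes alike, "correcting for the six tests within each outcome and controlling the false discovery rate at 0.05".
- **General Principles:** "We will use a two-sided critical alpha of 0.05 to conduct all statistical tests".

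No section describes an overall test of label type.

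**The concern.** A nonsphericity correction has a role only in a repeated-measures F test with more than two levels. Its presence among the inputs suggests that the power was calculated for an overall test of four means. An overall test pools evidence across three degrees of freedom, so its power does not carry over to any one pairwise difference, still less to one tested under a six-test correction.

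The paragraph is the only justification given for about 60 participants, and a reader will take 0.27 as the sensitivity of the comparisons listed in the hypotheses. If the real sensitivity is weaker, a non-significant icon versus text-only or pictorial versus icon result could be over-read as evidence of no difference.

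**Working it through.** **Inputs.** N = 60, m = 4 measures, correlation ρ = 0.60, nonsphericity correction 1, d = 0.27 and 80% power (Sample Size Needs); two-sided α = 0.05 (General Principles); six tests per outcome under Benjamini-Hochberg (BH) at 0.05 (Analyses of the secondary outcomes). Assumptions added here: d is in units of the single-condition SD, all pairs of conditions share ρ = 0.60, and there are 60 complete cases.

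**1. Reproducing the plan's figure.** For the within-subject F test, λ = f²·N·m/(1 − ρ), with 3 and 3 × 59 = 177 df.

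- With f = d/2 = 0.135: λ = 0.018225 × 60 × 4 / 0.40 = 10.935, and power is 79.2%.
- Power of exactly 80% at N = 60 needs f = 0.1363, so 2f = 0.2726, which rounds to the stated 0.27.
- Other readings do not fit. Taking f = 0.27 gives over 99.9%; a two-sided pairwise contrast gives 63–65%; a one-sided contrast about 75%; d standardised by the SD of the differences gives 54–55%.

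The F test with d = 2f is therefore the reading that reproduces the figure. This is an inference, since the plan does not name the test.

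**2. Power of one planned contrast at d = 0.27, unadjusted.** The SD of a within-person difference is √(2(1 − ρ)) = √0.80 = 0.894. The noncentrality is 0.27 × √60 / 0.894 = 2.338.

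| Reference distribution | Power |
|---|---|
| Model-based t, 177 df | 64.3% |
| Paired t, 59 df | 63.3% |
| Normal approximation | 64.7% |

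An 80% chance of detecting this contrast would need 87 participants (model-based t) to 89 (paired t). At N = 60 the d detectable with 80% power is 0.33 (0.325 and 0.329 on the two t tests).

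**3. Adding BH over six tests.** A BH threshold never exceeds 0.05, so step 2 is a ceiling. The loss depends on the other means. Simulation with 200,000 replicates per pattern and t with 177 df gave:

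| Means: control, text, icon, pictorial | Contrast | Power after BH |
|---|---|---|
| 0, 0.27, 0.54, 0.81 | each adjacent pair (0.27) | 62% |
| 0, 0, 0.27, 0.27 | each non-null pair | 50% |
| 0, 0.27, 0.27, 0.27 | each label vs control | 47% |
| 0, 0.09, 0.18, 0.27 | pictorial vs control | 42% |

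At the strictest BH step (α = 0.05/6 = 0.00833) power is 37%, a worst case.

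The second row is the pattern in which d = 2f equals the range of the means. Omnibus power there is 79%, yet each real pairwise difference is found half the time. That pattern is not the ordering in Hypothesis 1. In the third row even the omnibus test has only 66% power.

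**4. Detectable d at 80% power after BH.** About 0.33 for adjacent contrasts with equal ordered steps; 0.37 for label versus control when the three labels are equal; 0.39 for the largest contrast when equally spaced means span that range; 0.41 at the strictest step. At d = 0.5, power at the strictest step is 95%.

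**The case against.** - **The stated figure is right for its own test.** This is true: 79.2% is 80% to rounding. If d only means 2f, it describes the spread of four means, and setting a 20% miss rate beside a pairwise one compares different quantities. With f = 0.135 and equally spaced means in the hypothesised order, the range is 0.36, and pictorial versus control has 88% power unadjusted and 73% after BH. Adjacent contrasts in that pattern, however, have about 12% after BH. The plan does not tell the reader that d is a spread measure, and its hypotheses concern pairs.
- **The ceiling depends on ρ and on the reference distribution.** This stands as a condition. The normal approximation gives 64.7%, and ρ = 0.70 would give 77%. The 64% applies at the plan's own ρ of 0.60.
- **BH may cost almost nothing.** Under equal ordered steps the loss is about two points. If pictorial exceeds text by 1.74 and text exceeds control by 0.5 (an assumed value), a single adjacent gap of 0.27 keeps its 64%. The lower figures belong to other patterns, which are scenarios and not forecasts. The 64% itself does not depend on them.
- **The 1.74 says something about icon too.** For dwell time, if icon lies between text and pictorial, the two gaps sum to 1.74, so at least one is 0.87 or more. That is fair, but the other gap may still be small, and the figure says nothing about the other outcomes.
- **Nothing in the conduct of the trial changes.** This is correct, and it is why the remedy is confined to one paragraph.

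**Conclusion.** The concern holds. The 80% at d = 0.27 is a property of a test that is absent from the plan. The six contrasts that are planned have about 64% power at that difference before correction, so roughly 36% of such differences would be missed, against the 20% a reader would infer. Benjamini-Hochberg lowers power further by an amount that ranges from negligible to more than 20 points, depending on the pattern of means. The accurate detectable effect is 0.33 unadjusted and 0.33 to 0.41 after correction.

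This rests on N = 60 complete cases, ρ = 0.60 for every pair, and d on the single-condition SD. Standardising by the SD of differences makes it worse (54–55%). The plan uses complete cases and states no allowance for loss, so realised power could be lower still. That the figure came from an omnibus test is inferred; the shortfall in pairwise power does not depend on that inference. Effects of 0.5 or more are not at risk. It should be fixed, because it is the only justification of the sample size.

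**What to change.** Keep the sample size at about 60. In Sample Size Needs, name the test and standardiser behind the calculation and restate sensitivity for the planned contrasts, for example:

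> With 60 participants and a within-person correlation of 0.60, each pairwise contrast has 80% power to detect d = 0.33 (single-condition SD) at an unadjusted two-sided 0.05. After Benjamini-Hochberg correction over six tests, the detectable d depends on the other contrasts: about 0.33 for adjacent contrasts under equally spaced, ordered means, about 0.37 if the three labels differ equally from control and not from each other, and 0.41 at the strictest step. At d = 0.27 the power of a single contrast is about 64% before correction.

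A shorter version giving only the unadjusted 0.33 and the strictest-step 0.41 would also do. Limit the statement that the effect size is conservative to pictorial versus text on dwell time.

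The cost is one rewritten paragraph and a less favourable stated sensitivity (0.33–0.41 in place of 0.27). Recruitment and analysis are unchanged.

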### **Exclusions and Outliers**

We do not expect any outliers on survey measures because the Likert-style response options are constrained. We do not plan to exclude outliers for eye tracking outcomes, as is typical for eye tracking studies.
